9.6. Data Management

All data management and analysis will be conducted using Statistical Analysis System (SAS) version 9.4 (SAS Institute Inc., Cary, NC) and SAS Enterprise Guide 6.1 or later. The data will be extracted from the ORD once. The report will include the structured ORD and MA-PD data only.

9.7. Data Analysis

9.7.1. Propensity Score Modeling

Propensity scores that discriminate between receipt and non-receipt of RZV will be created from a wide variety of baseline demographic, comorbidity, disease severity (based on proxies for disease severity, such as treatment with advanced therapy), and comedication indicators. The propensity scores will be used to calculate IPTW to adjust for potential confounding in the comparative analysis.

There will be 4 propensity score models that, separately, will estimate propensity scores that discriminate between (1) receipt of two doses of RZV and non-receipt of RZV in UC cohorts, (2) receipt of two doses of RZV and non-receipt of RZV in RA cohorts, (3) receipt of at least one dose of RZV and non-receipt of RZV in UC cohorts, and (4) receipt of at least one dose of RZV and non-receipt of RZV in RA cohorts. If there are confounders identified that would only be appropriate to include in one model and not the other, separate propensity score models for the outcomes HZ and disease flare will be considered.

Propensity score modeling will be performed to determine and analyze the predictors of RZV receipt, incorporating dozens of predictors of vaccination status (such as age, sex, comorbidities, and concomitant medications). Propensity scores will be estimated using logistic regression that includes predictors of vaccination, including pre-specified covariates (ie, covariates included in [Section 9.3.6.1 – 9.3.6.4](#)) and empirically identified covariates based on the most frequently occurring diagnoses, procedures, and medications dispensed, as independent variables in the model and receipt of 2 doses of RZV/non-receipt (or receipt of at least 1 dose of RZV/non-receipt) as the dependent variable. Only covariates assessed during the 365-day baseline period and known (or highly suspected) to be confounders will be included in the propensity score model. The list of empirically identified covariates will be reviewed, and those covariates that are known risk factors of HZ or UC/RA disease flares will be identified and considered for inclusion in the propensity score model. Those covariates that are correlates of RZV receipt but are not risk factors for the outcomes (and therefore not confounders) will be removed from consideration. Some pre-specified

covariates may be closely correlated with the empirically identified variables. For variable pairs that are highly correlated (eg, correlation >0.9), one will be eliminated (retaining pre-specified covariates where possible). In addition, age, sex, and the interaction between age and sex will be included in the model to ensure adequate control of confounding by these variables. Additional details on model selection will be described in the SAP.

For a patient with a given covariate pattern, the propensity score will be the fitted value of the probability of that patient being a member of the RZV 2-Dose or RZV ≥ 1 Dose cohorts, given membership in the study population and the covariate pattern. To the extent that the decision to receive RZV for a particular patient depends on the health characteristics of the patient at the time of the decision, the propensity score models the clinical decision-making process. Additional details on the propensity score models will be described in the SAP.

Once the final models have been generated, propensity scores will be estimated for each patient.

Optum has extensive experience with propensity scores and has been involved in methodological development, application and explanations of the propensity score.^{28,29,30,31}

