To assess the effectiveness of RZV among patients treated with tofacitinib, the primary outcome for this study is the occurrence of new HZ infection. Occurrences of new HZ infection will be identified by the presence of a diagnostic code in claims for HZ infection after the second dose of RZV in the primary objective and after the first dose of RZV in the secondary objective. To assess the safety of RZV among patients treated with tofacitinib, the secondary outcome for this study is disease flare after the first dose of RZV: UC flare within the UC cohorts and RA flare within the RA cohorts. Occurrences of disease flare will be defined based on claims-based indicators and informed by review of the published literature.

Propensity scores that discriminate between receipt and non-receipt of RZV will be created from a wide variety of baseline demographic, comorbidity, disease severity (based on proxies for disease severity, such as treatment with advanced therapy), and comedication indicators, as well as risk factors for HZ. The propensity scores will be used to calculate inverse probability of treatment weights (IPTWs) to adjust for potential confounding in the comparative analysis. The main analysis for this project will estimate the incidence of the primary and secondary outcomes within the weighted cohorts, comparing those with RZV receipt to those without RZV receipt, yielding estimates of RZV effectiveness (primary and secondary outcomes) and safety (secondary outcomes) in those treated with tofacitinib. The main comparison will be among the subgroup of patients whose treatment with tofacitinib overlaps with both doses of RZV relative to patients treated with tofacitinib who do not receive RZV, as sample size allows. All analyses will be performed separately within the UC and RA cohorts.

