9.2.3.2. Exposure Cohorts

9.2.3.2.1. RZV 2-Dose Analysis

The RZV 2-dose analysis will be used to assess the primary objective for effectiveness.

Using UC patients as an example, patients who are current users of tofacitinib will be identified into the following 2 cohorts, based on receipt of RZV, as illustrated in [Figure 1](#):

1. UC RZV 2-Dose: UC patients who receive two doses of RZV; and

2. UC Comparator 2-Dose: UC patients who do not receive RZV and are time-matched (within a 4-week window) to patients in the UC RZV 2-Dose cohort.

Exposure cohorts among patients with RA will be identified using the same framework.

[figure not shown]
9.2.3.2.1.1. RZV 2-Dose Cohorts

Starting at the beginning of the study period (20 October 2017), Optum will identify the RZV 2-Dose cohorts by searching the pharmacy and medical claims records for RZV administrations among patients who are current users of tofacitinib (as defined in Section 9.2.3.1). Specifically, administrations of RZV that occur during tofacitinib on-treatment periods will be identified, as illustrated in Figure 3. A RZV administration will be defined as a second dose if a separate RZV administration is observed in the previous 1 to 6 months.⁹ Exposure to RZV will be identified as described in Section 9.3.4.

The RZV 2-Dose cohorts (UC or RA) will include patients who receive a second dose of RZV with the second dose occurring during a tofacitinib on-treatment period on or after the study initiation date. In the RZV 2-Dose cohorts, *the date of cohort entry will be set as the date of the second administration of RZV*. Additionally, to be eligible for the study, patients will have to fulfill additional criteria, as described in Sections 9.2.1 and 9.2.2.

While current tofacitinib exposure will be required at cohort entry (ie, receipt of second dose in the RZV 2-Dose cohort), the first dose of RZV will not be required to occur during a tofacitinib on-treatment period to be eligible for the RZV 2-Dose cohort. As shown in Figure 3, both example Patient 1 and Patient 2 are eligible for the RZV 2-Dose cohort at the time of receipt of the second RZV dose. Nonetheless, the main comparison will be the subgroup of patients whose treatment with tofacitinib overlaps with both doses of RZV relative to patients treated with tofacitinib who do not receive RZV (Section 9.7.3.1)

Figure 3. Examples of Patients Eligible for the RZV Cohort and/or Comparator Cohort

Tofacitinib exposed person-time

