 Non-tofacitinib exposed person-time
★ First RZV administration
★ Second RZV administration

[figure not shown]
9.2.3.2.1.2. Comparator 2-Dose Cohorts

In a similar fashion to the identification of the RZV 2-Dose cohorts, Optum will identify a cohort of patients without exposure to RZV among patients who are current users of tofacitinib. To minimize the immortal time bias that may be introduced when exposure is defined based on information accrued during follow-up,¹⁴ these patients will be randomly drawn from time-matched vaccination risk sets that are defined as sequential 4-week windows during which they were eligible for inclusion in the RZV cohorts, but without any RZV exposure during the window. Matching within this narrow caliper of calendar time limits the potential immortal time introduced by using future information (ie, lack of RZV receipt) to classify patients at the time of cohort entry. A cohort entry date will be randomly selected from this time window. In addition, other factors, such as duration of tofacitinib use, will be considered for matching upon feasibility, which will be described in the statistical analysis plan (SAP).

To construct the vaccination risk sets, separate 4-week windows will be created, starting on the study initiation date (20 October 2017) through the end of the study period. Among patients who are current tofacitinib users within a given 4-week window, patients without any RZV exposure who meet the study inclusion criteria (Section 9.2.1) and exclusion criteria (Section 9.2.2) at the beginning of the 4-week window will be identified. These patients will be eligible to be sampled as comparator patients for each RZV initiator identified with receipt of a second RZV dose during the same 4-week window. For example, as illustrated in Figure 4, patient A at the time of second RZV dose was eligible to be matched to comparator patient B and D during risk set #1, and similarly, patient B at the time of second RZV dose was eligible to be matched to comparator patient D and E during risk set #2.

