9.7.2. Inverse Probability of Treatment Weighting

The propensity scores will be used to calculate IPTW and weight each patient in the exposure cohorts. This will be performed separately for the RZV 2-Dose and RZV ≥ 1 Dose analyses. IPTW produces weighted groups that have similar patterns of the presence or absence of a large number of factors. With IPTW, the balance between the comparison cohorts can be expected to be similar to or better than would be achieved in a randomized trial with respect to all identified covariates. Matching on the propensity score will be considered as an alternative approach, but IPTW has the advantage that fewer eligible patients would be excluded due to their inability to match.

The IPTW will be defined such that the causal estimate is the average treatment effect in the treated (ATT).³² Two sets of IPTW will be estimated, one for the UC cohorts and one for the RA cohort. Briefly, to estimate the ATT, the weights are defined such that every RZV-exposed patient receives a weight of one, while the unexposed patients receive weights that are a function of the propensity score:

$$w_{ATT} = Z + \frac{e(1-Z)}{1-e}$$

where Z is the indicator for RZV exposure and e is the propensity score,

$$e = \Pr(Z = 1|X).$$

The propensity score is the probability of receiving RZV as a function of \mathbf{X} , a vector of the predictors of RZV exposure.

Balance of covariates among the IPT weighted cohorts will be assessed using the standardized difference (SD) comparing the weighted study cohorts. Any variables with an absolute SD >0.1 may be considered imbalanced. If specific variables remain imbalanced after weighting, they will be included as independent predictors in outcome models. Overall balance between the cohorts, both before and after weighting, will be assessed via overlap (or lack thereof) in histograms of the weights. Trimming of extreme weights will be considered.³³

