9.7.3.1. RZV 2-Dose Analysis

The RZV 2-dose analysis will be used as the main analysis for assessment of the primary objective for effectiveness. Incidence rates and corresponding 95% confidence intervals for the primary outcome (HZ) will be calculated before and after weighting. All analyses will be performed separately within the UC and RA cohorts. The incidence rate of HZ in the RZV 2-Dose cohort will be compared to the Comparator 2-Dose cohort. Weighted Kaplan-Meier plots will be used to depict the cumulative probability of survival (non-occurrence of the event).

Given the sampling approach that will be utilized in this study (sampling with replacement), we will calculate the number of patients that were selected and included in a study cohort more than once (Section 9.2.3.2.1). If that number exceeds 10% of the study population, then covariance between observations will be taken into account using an appropriate method (eg, generalised estimating equations or robust variance estimators).

The relative hazard will be calculated through weighted Cox regression models with appropriate 95% confidence intervals. Known confounders that are strongly associated with RZV receipt and HZ may also be included in the regression models as well as any variables with an absolute SD >0.1 between weighted exposure cohorts. Additional details on model selection will be detailed in the SAP.

Patients will be further stratified by the following patient groups relative to their matched comparators:

1. Tofacitinib current users at time of receipt of first and second RZV doses;
2. Tofacitinib current users at time of receipt of second RZV dose only.

The first subgroup analysis conducted among patients who receive two doses of RZV and are current users of tofacitinib at the time of receipt of both doses will be the main comparison.

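### The propensity models and ATT weights target all two-dose vaccinees, not the both-doses tofacitinib subgroup that forms the main comparison, and a histogram of ATT weights cannot show overlap

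*Protocol*

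**What the plan says.** - **Main comparison.** Section 9.1 states: "The main comparison will be among the subgroup of patients whose treatment with tofacitinib overlaps with both doses of RZV". Section 9.7.3.1 repeats that vaccinees who "are current users of tofacitinib at the time of receipt of both doses will be the main comparison". It forms this group by stratifying vaccinees and carrying their matched comparators along.
- **The 2-Dose cohort is wider.** Under Section 9.2.3.2.1.1, "the first dose of RZV will not be required to occur during a tofacitinib on-treatment period to be eligible for the RZV 2-Dose cohort".
- **Propensity models.** Section 9.7.1: "There will be 4 propensity score models that, separately, will estimate propensity scores that discriminate between" four pairs of groups. The first is "receipt of two doses of RZV and non-receipt of RZV in UC cohorts"; the others are its RA counterpart and the two at-least-one-dose contrasts. The only further models foreseen are separate ones for HZ and for flare.
- **Weights and balance.** Section 9.7.2 uses ATT weights: 1 for each RZV patient and e/(1 − e) for each comparator. Standardized differences are computed on the weighted study cohorts, with a limit of 0.1. Overall balance, before and after weighting, "will be assessed via overlap (or lack thereof) in histograms of the weights".
- **Comparators.** Section 9.2.3.2.1.2 draws them from a pool described as "Among patients who are current tofacitinib users within a given 4-week window", where the window is the one containing the vaccinee's second dose. Matching on tofacitinib duration is optional and deferred to the SAP.
- **Covariates.** Section 9.3.6.4 lists tofacitinib average daily dose, cumulative dose and treatment duration. Section 9.7.1 draws on this list for the propensity models.

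**The concern.** ATT weights make comparators resemble the treated group that was modelled. Here that group is every two-dose vaccinee, but the headline estimate keeps only those on tofacitinib at both doses. That selection is made on tofacitinib history, so the two vaccinee groups are likely to differ in duration, cumulative dose and whatever goes with them. Weights aimed at their mixture miss the subgroup.

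The comparator rule can push the same way. A both-doses vaccinee was also a current user at the first dose, 1 to 6 months earlier (up to 7 with the grace period in Section 9.3.4). A comparator need be a current user only in the dose-2 window and may have started recently.

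At stake is the primary HZ hazard ratio. Section 9.7.4 plans to look for a dose-response between tofacitinib exposure and the outcomes, so the plan itself treats exposure history as possibly prognostic. The overlap plot would give no warning.

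**Working it through.** The protocol gives no figure for this point except the 0.1 limit, so there is nothing to reproduce first.

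**1. Leftover imbalance in the main comparison**

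Let s be the share of two-dose vaccinees on tofacitinib at both doses. Let m_B and m_D be the covariate means, in SD units, in the both-doses and dose-2-only groups.

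- Full-cohort ATT weights bring comparators to the mean of all two-dose vaccinees: s·m_B + (1 − s)·m_D.
- The subgroup's own mean is m_B.
- The difference is m_B − s·m_B − (1 − s)·m_D = (1 − s)(m_B − m_D), that is, **(1 − s) × gap**.

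This assumes that the subgroup's matched comparators have about the same weighted mean as all comparators. That is reasonable when matching is on calendar window and data source only. The protocol states neither s nor the gap, so the table is a range of assumptions:

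| Both-doses share s | gap 0.25 | gap 0.5 | gap 1.0 |
|---|---|---|---|
| 0.9 | 0.025 | 0.05 | 0.10 |
| 0.8 | 0.05 | 0.10 | 0.20 |
| 0.7 | 0.075 | 0.15 | 0.30 |
| 0.5 | 0.125 | 0.25 | 0.50 |

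The 0.1 limit is passed when gap > 0.1/(1 − s): above 1.0 at s = 0.9, 0.5 at s = 0.8, 0.33 at s = 0.7 and 0.2 at s = 0.5.

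**2. Simulation check**

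Assumptions: 200 runs, 1,500 vaccinees, two comparators each, s = 0.75, gap 1.2 SD, logistic propensity model with linear and squared terms. Mean standardized differences:

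- full-cohort weights, full cohort: 0.005
- full-cohort weights, both-doses subgroup: 0.30 (formula: 0.25 × 1.2 = 0.30)
- model fitted within the subgroup: 0.000

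So the full-cohort balance table can look clean while the main comparison is at three times the limit.

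**3. Overlap plot**

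Every RZV weight is 1, so the RZV histogram is a single spike. At two comparators per vaccinee with no confounding, e = 1/3 and every comparator weight is (1/3)/(2/3) = 0.5. The histograms then do not touch, although overlap is perfect. Results with increasing separation of the groups on a simulated confounder:

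| Separation (SD) | Overlap of propensity-score histograms | Overlap of ATT-weight histograms |
|---|---|---|
| 0 | 1.00 | 0.000 |
| 0.5 | 0.80 | 0.021 |
| 1 | 0.61 | 0.020 |
| 2 | 0.32 | 0.008 |

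The weight plot stays near zero throughout, so it cannot tell good overlap from poor. Before weighting there are no weights to plot.

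**The case against.** **Safeguards exist.** A reader might infer that optional matching is the only control on tofacitinib history. It is not: dose and duration are listed propensity covariates, and variables above the 0.1 limit are added to the outcome model. This stands and narrows the point. The protocol describes these tools for the full weighted cohorts and does not say that they are repeated in the subgroup.

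**The SAP may settle it.** Section 9.7.1 defers modelling detail to the SAP, and the amendment table's entry for Section 9.7 mentions subgroup analyses alongside separate models. The protocol also never says outright that full-cohort weights are reused in the subgroup. But it does fix the number and targets of the models, and none is for the main comparison. An SAP that follows the list inherits the problem, and the amendment entry is ambiguous and is not operative text.

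**The size is unknown.** This stands. It is tempting to size the problem from the median of 11 dispensings in Section 9.5 and conclude that a given share of comparators were off drug at the dose-1 date. The figure does not support that. It describes vaccinated patients, counts fills per patient rather than the length of one on-treatment period, and says nothing about unvaccinated users. Section 9.2.3.1 also allows restarts, so a recently begun period does not prove earlier non-use.

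**The histogram is a supplement.** Also fair. Standardized differences work under ATT weights, comparator weights still reveal extremes, and the wording may be a slip for propensity scores. As written, though, the check cannot do its job.

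**Conclusion.** The point holds on the text. The 2-dose models and their ATT weights target all two-dose vaccinees, while the headline estimate concerns a subgroup selected on tofacitinib history, and no balance check is described for that subgroup. Under assumed values the leftover standardized difference runs from 0.025 (share 0.9, gap 0.25) to 0.50 (share 0.5, gap 1.0). Whether it passes 0.1 cannot be settled from the protocol. The comparator rule can add to an imbalance in duration, by an amount the protocol does not allow one to state.

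A reader might go further and conclude that the primary hazard ratio is biased. That is not shown: imbalance matters only so far as the covariate predicts HZ, and neither the direction nor the size of such an effect can be derived here.

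The overlap fault needs no assumption beyond the weight definition in Section 9.7.2. It is a smaller matter and easily corrected.

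**What to change.** 1. In Sections 9.7.1 to 9.7.3.1, state that the propensity score and ATT weights are estimated, and standardized differences reported, within the main-comparison subgroup and its matched comparators, separately for UC and RA. Apply the 0.1 adjustment rule there. Allow a reduced, pre-specified covariate set if a stratum is small.
2. In that comparison, align comparators on tofacitinib history. One option is to require current use on the date corresponding to the matched vaccinee's first dose; another is to match or adjust on duration within the subgroup.
3. In Section 9.7.2, replace the weight histograms with propensity-score distributions by cohort, before and after weighting. Keep comparator-weight histograms only to identify extreme weights.

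The cost is one extra logistic model and balance table per disease, on data already to be extracted, and some comparators under item 2. Numbers are a real limit. Section 9.5 counts 1,932 two-dose patients across both diseases before eligibility criteria, and Section 9.1 already makes the main comparison conditional on sample size. Hence the reduced covariate set and the choice of alignment method.

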9.2.4. Baseline Period

For each of the study cohorts, the baseline period will be defined as the 365 days prior to and including the cohort entry date. Recognizing that a narrower (for time-varying covariates, etc.) or broader (for chronic conditions, etc.) window of assessment may better capture select patient attributes of interest, select covariates may be assessed using alternate time period(s). Patients selected into more than one cohort (eg, RZV ≥ 1 Dose and RZV 2-Dose cohorts) will have separate baseline periods corresponding to each date of cohort entry.

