9.3.6. Covariates

Members of the study cohorts will be described according to claims-based covariates. Unless otherwise specified, diagnoses will be identified through the presence of ICD-10 codes, while prescription medications will be identified through pharmacy dispensings or administrations. No over-the-counter medications will be assessed. Drug use and disease status will be

² CPT copyright 2022 American Medical Association. All rights reserved.

categorized as yes (code present) or no (no code present). Demographic attributes will be determined on the cohort entry date while other factors will be assessed during the 365-day baseline period, unless otherwise specified. In addition to the covariates listed below, the 50 most common diagnoses, procedures, and medications will be described during the baseline period.

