9.3.6.4. Treatment History

- Tofacitinib treatment;
 - Tofacitinib dose;
 - Average daily dose in prior 91 days;
 - Cumulative dose in prior 365 days;
 - Treatment duration;
- Zostavax[®] vaccination;
- TNF inhibitor treatment (eg, etanercept, adalimumab, golimumab, infliximab, certolizumab);
- Non-TNF biologics (eg, abatacept, rituximab, tocilizumab, sarilumab, anakinra, ustekinumab, vedolizumab);
- csDMARD treatment (eg, methotrexate, sulfasalazine, hydroxychloroquine, leflunomide, azathioprine);
- Immunosuppressants (eg, azathioprine, 6-mercaptopurine, cyclosporine);
- JAK inhibitor treatment (eg, baricitinib, upadacitinib);
- Corticosteroid treatment;
 - Average daily dose (eg, None, ≤ 5 mg/day, >5 to ≤ 10 mg/day, >10 to ≤ 20 mg/day, and >20 mg/day of prednisone average dose equivalent);
 - During 30 days prior to cohort entry;
 - During 365 days prior to cohort entry;
- Number of treatments for UC/RA prior to cohort entry;
- Chemotherapy;
- Radiotherapy;
- 5-aminosalicylates (eg, mesalamine, balsalazide, olsalazine);
- Ozanimod.

Additional therapies that are approved for the treatment of UC or RA may be incorporated if they become available. All of the above covariates may be considered for inclusion in the propensity score model used for IPTW.

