Figure 6. Upper Bound of Vaccine Effectiveness for a Range of Population Sizes and Vaccine Effectiveness Estimates

Assumptions: 1.2% HZ rate in unexposed; 2:1 matching of comparators to RZV exposed patients²⁷

Table 2. Prevalence of Zostavax Vaccination and Duration of Enrollment Among Adults (18+) with RA or UC Treated with Tofacitinib and Shingrix: Optum Claims Database, October 2017 to July 2022

	Patients with Tofacitinib and Shingrix	
	Patients <60 years of age N (%)	Patients ≥60 years of age N (%)
Total patients	649 (100.0%)	1,248 (100.0%)
Patients with a claim for Zostavax^a	16 (2.5%)	94 (7.5%)
With at least 1 year of enrollment prior to Shingrix ^a	544 (83.8%)	1,069 (85.7%)
Patients with a claim for Zostavax^b	16 (2.9%)	87 (8.1%)
With at least 2 years of enrollment prior to Shingrix ^a	437 (67.3%)	859 (68.8%)
Patients with a claim for Zostavax^b	15 (3.4%)	83 (9.7%)
With at least 3 years of enrollment prior to Shingrix ^a	340 (52.4%)	667 (53.5%)
Patients with a claim for Zostavax^b	13 (3.8%)	74 (11.1%)
With at least 4 years of enrollment prior to Shingrix ^a	264 (40.7%)	519 (41.6%)
Patients with a claim for Zostavax^b	10 (3.8%)	68 (13.1%)
With at least 5 years of enrollment prior to Shingrix ^a	205 (31.6%)	388 (31.1%)
Patients with a claim for Zostavax^b	7 (3.4%)	52 (13.4%)

^a Denominator for percent is the number of patients in the relevant age category (<60, ≥60).

^b Denominator for percent is the number of patients with the duration of enrollment (eg, 1, 2, etc) in the row above.

The prevalence of prior Zostavax vaccination and duration of enrollment among UC and RA patients treated with tofacitinib and Shingrix is shown in [Table 2](#). Among patients under age 60 years, 2.5% had prior exposure to Zostavax whereas 7.5% of patients 60 years of age and older had Zostavax exposure. Regarding duration of enrollment prior to receipt of Shingrix, over 80% of patients in both age groups had at least 1 year, while slightly more than 30% had at least 5 years of enrollment.

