As patients that have UC and RA may have different clinical characteristics compared to patients that have only one of the two diseases, the number of patients that have both diagnoses will be quantified. Additionally, a sensitivity analysis will be conducted in which the association between RZV exposure and the primary and secondary outcomes is assessed after excluding patients with both UC and RA from the exposure cohorts.

To assess the effect of prior Zostavax vaccination on subsequent RZV effect, an analysis will be performed where the study population is restricted to patients with at least 5 years of enrollment prior to cohort entry. Within this subset, the analysis will be conducted separately among patients with and without Zostavax vaccination during this baseline 5-year period. The effect of prior Zostavax exposure will be informed by the extent to which the estimate of RZV effect differs according to strata of prior Zostavax exposure.

It is possible that the comparator cohorts could include patients previously vaccinated with RZV more than 365 days earlier. To address this potential exposure misclassification, a sensitivity analysis will be performed, for which the study population will be restricted to patients with enrollment that extends back to 20 October 2017 and who do not have any prior administration of RZV during that time. Finally, a sensitivity analysis will be conducted for HZ in which patients are stratified based on their amount of available follow-up time.

Misclassification of disease flares is possible when using claims-based algorithms (for example, patients may change therapy for reasons other than disease flares), leading to over- or under-estimation of the outcome; thus, alternative definitions will be explored and outlined in the SAP as sensitivity analyses. Specifically, sensitivity analysis will explore using a more conservative definition based on only UC-related surgeries or ER and hospitalizations with UC or RA as the primary diagnosis, as well as evaluating more expansive definitions inclusive of other medications of interest, such as biologics or other JAK inhibitor treatments.

Additional sensitivity analysis may be performed if needed.

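### Section 9.7.1 confines the propensity score to 365-day covariates, so balance on earlier Zostavax is not assured in the main analysis, and anti-herpes antivirals are not a pre-specified covariate

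*Protocol*

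**What the plan says.** - **Covariate list.** Section 9.3.6.4 (Treatment History) includes "Zostavax[®] vaccination" and gives it no window. The default in section 9.3.6 is that "other factors will be assessed during the 365-day baseline period, unless otherwise specified".
- **Flexibility.** Section 9.2.4 recognises that a narrower or broader window may suit some attributes: "select covariates may be assessed using alternate time period(s"). It does not say which covariates.
- **Propensity score.** Section 9.7.1 then sets the entry rule: "Only covariates assessed during the 365-day baseline period and known (or highly suspected) to be confounders will be included in the propensity score model".
- **Table 2 (section 9.5).** It gives the number of patients with a Zostavax claim by minimum length of enrollment, up to the row "With at least 5 years of enrollment prior to Shingrix". It covers only tofacitinib users who received Shingrix and gives no dates for the Zostavax claims.
- **Sensitivity analysis (section 9.7.4).** To see how prior Zostavax affects the RZV effect, "the study population is restricted to patients with at least 5 years of enrollment prior to cohort entry", and the analysis is "conducted separately among patients with and without Zostavax vaccination during this baseline 5-year period".
- **Antivirals.** No systemic anti-herpes antiviral is named among the covariates, current treatments, exclusions, censoring rules or sensitivity analyses.

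**The concern.** Sections 9.2.4 and 9.7.1 conflict. The first lets a covariate be measured over a longer window. The second admits to the score only what is measured in the 365-day baseline. A patient vaccinated with Zostavax two or more years before entry is then coded as never vaccinated in the model that produces the weights.

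The planned diagnostics would not show this. Standardized differences (section 9.7.2) are computed on the covariate as measured, so a one-year Zostavax flag can look balanced while earlier vaccination is not.

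Zostavax and anti-herpes antivirals both bear on the risk of herpes zoster, and either could plausibly differ between patients who do and do not receive RZV. If so, part of the estimated RZV effect would belong to them. Claims for both would sit in the medical and pharmacy data that the study already uses.

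**Working it through.** **1. Reproduce Table 2.** The percentages follow from the counts (for example 87/1,069 = 8.1% and 52/388 = 13.4%), except one last-digit difference: 667/1,248 = 53.4%, printed as 53.5%.

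**2. Separate the bands.** Each row contains all longer-enrolled patients, so it mixes long and short look-backs. The cumulative rows alone would suggest 1 - 8.1/13.4 = about 40% missed, which is too low for that reason. Subtracting adjacent rows gives:

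| Enrollment before Shingrix | Age ≥60: Zostavax claim | Age <60: Zostavax claim |
|---|---|---|
| <1 year | (94-87)/(1,248-1,069) = 7/179 = 3.9% | (16-16)/(649-544) = 0/105 = 0% |
| 1 to <2 years | (87-83)/(1,069-859) = 4/210 = 1.9% | (16-15)/(544-437) = 1/107 = 0.9% |
| ≥5 years | 52/388 = 13.4% | 7/205 = 3.4% |

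**3. Share missed, age ≥60.** The formula is 1 - (short-band prevalence / ≥5-year prevalence).
- 1 to <2 years: 1 - 1.9/13.4 = about 86%. Fisher's exact p for 4/210 against 52/388 is 6e-7. The exact 95% intervals are 0.5%-4.8% and 10.2%-17.2%.
- <1 year: 1 - 3.9/13.4 = about 71%.

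Under age 60 the comparison rests on 1 claim against 7 (p = 0.27) and settles nothing. Patients aged ≥60 are 1,248 of the 1,897 in Table 2 (66%).

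**4. What the 5-year analysis retains.** RZV recipients with ≥5 years: 205 + 388 = 593, or 593/1,897 = 31%. With Zostavax: 7 + 52 = 59. Without: 593 - 59 = 534. These counts precede the UC/RA split, the two-dose requirement (70% of recipients in Table 1) and the requirement of tofacitinib at both doses. Assume 2 years of follow-up each and the section 9.5 rate of 1.2 per 100 person-years. The Zostavax stratum then gives 59 × 2 = 118 person-years, and expected RZV-arm cases of 118 × 0.012 × 0.15 = 0.2 at 85% effectiveness, or 118 × 0.012 = 1.4 at no effectiveness.

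**5. Size of the possible bias.** The documents give neither the Zostavax prevalence in comparators nor its residual protection, so these are assumptions. With prevalence p1 in vaccinees, p0 in comparators and Zostavax hazard ratio h, the bias factor on the rate ratio is

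BF = (1 - p1 + p1·h) / (1 - p0 + p0·h), and corrected VE = 1 - (1 - observed VE)/BF.

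| p1 | p0 | h | BF | VE if 66.7% observed | VE if 85% observed |
|---|---|---|---|---|---|
| 13.4% | 0% | 0.3 | 0.906 | 63.3% | 83.4% |
| 13.4% | 5% | 0.5 | 0.957 | 65.2% | 84.3% |
| 10% | 5% | 0.5 | 0.974 | 65.8% | 84.6% |
| 10% | 10% | any | 1.000 | 66.7% | 85.0% |
| 10% | 15% | 0.3 | 1.039 | 68.0% | 85.6% |

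The 10% is close to the all-age figure of 59/593 = 9.9%. The table treats all Zostavax as uncontrolled. The one-year flag would control part of it, so these are outer values for the assumptions shown.

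**6. Antivirals.** The documents contain no figure on their use, so no size can be derived.

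**The case against.** **No imbalance is shown.** A reader might infer that the arms are unbalanced and that RZV effectiveness is overstated. The documents do not support that. Section 9.5 introduces Table 2 with "The prevalence of prior Zostavax vaccination and duration of enrollment among UC and RA patients treated with tofacitinib and Shingrix is shown in" Table 2, so it holds vaccinees only. Equal prevalence in both arms would give no bias, and a higher prevalence in comparators would reverse the sign. This objection stands in full.

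**Table 2 does not observe the miss.** Without claim dates, the 70-86% is an inference from patients with different lengths of enrollment. The <1-year band (3.9%) lies above the 1-to-<2-year band (1.9%), which points to noise or to bands that are not quite alike. That is why a range is given. The gap to 13.4% is still large, and the upper confidence limit of the 1-to-<2-year band (4.8%) lies well below the lower limit of the ≥5-year band (10.2%).

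**Other routes exist.** It would be too strong to say that the plan cannot adjust for these treatments. Section 9.7.3.1 lets known strong confounders enter the outcome model, section 9.7.1 screens frequent drugs for the score, and section 9.7.4 plans a bias analysis for incompletely captured covariates. All this is true, but the first is optional. The second depends on antivirals being among the most frequent drugs and being kept as known risk factors for the outcome. The third names only disease severity as its example.

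**The look-back is not one year throughout.** Section 9.7.4 uses 5 years, and its no-Zostavax stratum of about 534 RZV recipients is a useful check. It does not alter the main estimate.

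**Detail may sit in the SAP.** It may, but section 9.7.1 itself states an exclusive rule that contradicts section 9.2.4. The conflict is in the protocol.

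**Conclusion.** The point holds in a limited form. As written, section 9.7.1 restricts Zostavax in the main propensity score to 365 days and blocks the flexibility of section 9.2.4. If enrollment bands are otherwise comparable, that window misses roughly 70-86% of recorded recipients aged 60 or over; below 60 the data are too sparse to say. Balance on earlier Zostavax is therefore not assured.

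The direction is unknown. Over the assumed inputs, an observed effectiveness of 66.7% would correspond to about 63.3%-68.0%, and 85% to about 83.4%-85.6%. That is small beside the statistical uncertainty: section 9.5 places the upper confidence bound about 18 points above 66.7% at 2,000 vaccinated person-years. Unlike that uncertainty, however, the bias does not shrink with sample size.

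The section 9.7.4 analysis addresses effect modification in about 31% of vaccinees, and its Zostavax stratum is too small for an estimate. For antivirals, the finding is only that a treatment directed at the virus behind the primary outcome is not pre-specified. The change is worth making because it is cheap, not because a large bias has been shown.

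**What to change.** 1. In section 9.7.1, exempt Zostavax from the 365-day rule and reconcile the sentence with section 9.2.4. Define prior Zostavax as any claim in all available enrollment before cohort entry, and include length of prior enrollment in the model.
2. In section 9.3.6.4, add baseline systemic anti-herpes antiviral dispensing to the pre-specified covariates.
3. In section 9.7.4, keep the no-Zostavax stratum (5-year look-back) as the informative sensitivity analysis, and report the Zostavax stratum descriptively only.

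I would not add censoring at the start of an antiviral: it is a post-baseline event and the censoring could be informative.

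The cost is two covariate definitions and a change in how one stratum is reported, all from data sources already in the plan. The one drawback is that look-back length then varies between patients. The enrollment-length term addresses this, and the uniform 5-year stratum serves as a check.
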